Study Objectives	Primary Objective: To exploretheefficacyofTopicort®TopicalSprayatweeks4 and16 withrespectto Investigator GlobalAssessme nt(scalponly), Psoriasis ScalpSeverityIndex(PSSI) , andScalpSurfaceArea(SSA) Secondary Objectives: PGAxBSA,patient reportedoutcomes ,adverseevents
Study Design	A single center,observationalstudyof2 0subjectstoassess4weeksof therapy with Topicort® BIDand12weeks BIDontwoconsecutivedaysaweek patients with scalppsoriasis
Study Centers	PsoriasisTreatmentCenterofCentralNewJersey
Study Population	Adultmaleandfemalesubjectswithmoderatetoseverechronicplaque psoriasis
Main Inclusion Criteria	Subjectsmustmeetthefollowingcriteriatobenrolledinthisstudy: 1. Maleorfemaleadult \geq 18yearsofage; 2. Chronicscalppsoriasis \geq 30% 3. Investigator GlobalAssessment(scalponly) ofmildorgreater
Main Exclusion Criteria	Subjectswhomeetanyofthefollowingcriteriawillbeexcludedfrom participationinthisstudy: 1. Subjectswithnonplaquetypepsoriasis(e.g.guttate and erythrodermic). 2. Subjectswith<30%scalppsoriasis. 3. Useofprohibitedmedications duringstudyperiod.
Study Drug Dosage and Administration	Allpati entswillreceiveTopicort ® BIDfor4weeks. Afterweek4pat ientwillreceiveTopicort willreceiveTopicort® BIDontwo consecutivedaysaweek for12weeks . Patientswilltreatotherbodyareas affectedbyplaquepsoriasiswithTopicort®duringthestudyperiod(excludes face,groin,axilla)
Study Endpoints	Improvementafter 4and 16weeksof: InvestigatorGlobalAssessment(scalponly) PsoriasisScalpSeverityIndex Scalpsurfacearea Physician Global Assessment x Body Surface Area Pain,itching,scaling(scalponly) Scalpdex
Study Duration	16 weeks

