4. STUDY OBJECTIVE

To explore the effectiveness and safety of Topicort® Topical Spray for patients with scalp plaque psoriasis.

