5. INVESTIGATIONAL PLAN

5.1 Overall Study Design and Plan

20 subjects with at least mild scalp psoriasis and scalp surface area greater than or equal to 30%, will receive Topicort® twice daily for 4 weeks followed by twice daily two times a week for 12 weeks.

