5.2 Study Population Criteria

Males and females ≥ 18 years of age with plaque type scalp psoriasis

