5.2.1 Inclusion Criteria

Patients who meet all of the following criteria will be enrolled in the study:

1. Male or female adults ≥ 18 years of age.
2. Diagnosis of chronic plaque-type scalp psoriasis.
3. IGA of mild or greater (scalp only) determined at screening
4. Scalp surface area of 30% or greater determined at screening
5. Able to give written informed consent prior to performance of any study related procedures.
6. Females of childbearing potential (FCBP) must have a negative pregnancy test at Screening and Baseline. FCBP who engage in activity in which conception is possible must use one of the approved contraceptive options: hormonal contraception; intrauterine device (IUD); tubal ligation; or partner's vasectomy; Male or female condom, diaphragm with spermicide, cervical cap with spermicide, or contraceptive sponge with spermicide.
7. Subject must be in general good health (except for psoriasis) as judged by the Investigator, based on medical history, physical examination.

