5.2.2 Exclusion Criteria

Patients will NOT be enrolled in this study if they meet any of the following criteria:

1. <30% scalp surface area
2. Scalp IGA clear or almost clear at time of screening
3. Any condition, which would place the subject at unacceptable risk if he/she were to participate in the study.
4. Pregnant or breast feeding, or considering becoming pregnant during the study.
5. Use of any investigational drug within 4 weeks prior to randomization, or within 5 pharmacokinetic/pharmacodynamic half lives, if known (whichever is longer).
6. Use of oral systemic medications for the treatment of psoriasis within 4 weeks (includes, but not limited to, oral corticosteroids, methotrexate, acitretin, apremilast and cyclosporine).
7. Use of ustekinumab and/or anti-IL-17 biologic therapy within 24 weeks or other experimental or commercially available biologic immune modulator(s) within 12 weeks prior to the first IP dose.
8. Patient used other topical therapies to treat within 2 weeks of the Baseline Visit (not including permitted topical therapy for face, groin and axilla).
9. Patient received UVB phototherapy within 2 weeks of Baseline.
10. Patient received PUVA phototherapy within 4 weeks of Baseline.
11. Patient has a known hypersensitivity to the excipients of Topicort Spray® as stated in the label.

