5.4 Subject Enrollment and Treatment Assignment

20 subjects of either gender scalp plaque psoriasis will be enrolled to receive open-label Topicort® BID for 4 weeks followed by twice daily two days a week for 12 weeks.

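### Does the synopsis label of moderate to severe disease, or the odd printed wording of scalp IGA grade 1, change who is studied or how the results read?

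*Combined protocol and SAP*

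**What the plan says.** The synopsis gives the study population as "Adultmaleandfemalesubjectswithmoderatetoseverechronicplaque psoriasis". It attaches no scale to that severity and mentions neither the scalp nor the 30% scalp-area threshold. The next row of the synopsis, inclusion item 3, asks for an Investigator "GlobalAssessment(scalponly) ofmildorgreater".

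The body of the protocol keeps to the lower floor. Section 5.1 plans for "20 subjects with at least mild scalp psoriasis and scalp surface area greater than or equal to 30" per cent. Section 5.2.1 item 3 requires "IGA of mild or greater (scalp only) determined at screening". Section 5.2.2 item 2 removes only "Scalp IGA clear or almost clear at time of screening". Section 5.6.6 sets the entry score at 2. Other statements of the population give no severity at all: Section 4 ("To explore the effectiveness and safety of Topicort® Topical Spray for patients with scalp plaque psoriasis"), Section 5.2 ("Males and females ≥ 18 years of age with plaque type scalp psoriasis"), Section 5.4 ("20 subjects of either gender scalp plaque psoriasis will be enrolled") and the synopsis Study Design row.

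Appendix A defines the scalp IGA. Grade 0 requires that no sign of psoriasis be present. Grade 1 requires no thickening and, as printed, places a bare negative directly before the words for slight focal scaling. Grade 2 begins at barely detectable thickening with mainly fine scaling. The colour description in grade 3 also reads as if a joining word were missing. Section 5.6.6 says that the grade reflects the average degree of redness, induration and scaling.

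**The concern.** A population statement tells the reader to whom the conclusions apply. If a report copied the synopsis row, it would describe a sample with at least moderate disease, although subjects with mild scalp disease may enter. Adjacent rows of one table appear to disagree, and such a disagreement can lead two sites, or a site and an analyst, to apply different rules.

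The anchor wording looks more serious, because scalp IGA is both an entry criterion and one of the three measures in the primary objective. Any improvement from grade 2 has to cross the boundary between grades 1 and 2. If a common end-of-treatment appearance (flat, with a trace of scale) has no grade, raters could settle it differently, and in a study of about 20 subjects a few such choices would show in the summary.

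**Working it through.** The plan gives no figure to reproduce here. Section 8.2 states about 20 subjects, with no effect size, power or error rate. The check is therefore mainly a comparison of passages.

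**Label.** Statements bearing on severity at entry:

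- Moderate to severe, no scale named: synopsis Study Population row (1 place).
- Scalp IGA of mild admitted: synopsis inclusion item 3, Section 5.1, Section 5.2.1 item 3, Section 5.2.2 item 2, Section 5.6.6 (5 places).
- No severity term: Section 4, Section 5.2, Section 5.4, synopsis Study Design row (4 places).

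The outlier has no operative role. Section 5.6.2 determines eligibility by the inclusion and exclusion criteria, and these agree. Sections 5.6.8 and 5.6.9 measure whole-body PGA and BSA, but neither has an entry minimum. Section 8.2 defines no analysis set or subgroup by severity. Correcting the row would add no subject, remove none and alter no calculation.

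**Anchor.** Take a scalp of normal or pink colour, with no thickening and slight focal scaling, and read Appendix A literally:

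- Grade 0 fails, because a sign is present.
- Grade 1 as printed fails on scaling.
- Grades 2 to 4 fail, because each requires some thickening.

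The match is 0 of 5 grades. If grade 1 is read as a range from no scaling up to slight focal scaling, the same scalp falls in grade 1 only. Literal gaps remain after that repair: for example, no thickening with fine scaling, or light red colour without thickening. Repairing the anchor therefore does not make the descriptors exhaustive. The averaging rule in Section 5.6.6 is what handles mixed presentations, both for the repaired case and for those that remain.

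Apply that rule to the gap case. Absence of thickening points to grade 0 or 1. Normal to pink colour fits grade 1. A trace of scale lies between none and the fine scaling of grade 2. The nearest grade on average is 1, which is also what the evident intended wording gives.

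At entry the case is unlikely to arise: the subject would need at least 30% of the scalp involved, with no thickening and only slight focal scaling. The wording could matter mainly at follow-up.

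**Size.** One subject of 20 regraded across a cut-off moves a proportion by 1/20 = 5.0 percentage points. One subject moved by one grade shifts the mean IGA by 1/20 = 0.05. The plan does not define a responder proportion, so the following proportions are assumptions for scale only. Exact (Clopper-Pearson) 95% intervals at n = 20:

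| Assumed result | 95% interval |
|---|---|
| 5/20 = 25% | 8.7% to 49.1% |
| 10/20 = 50% | 27.2% to 72.8% |
| 15/20 = 75% | 50.9% to 91.3% |

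At 50% the interval is 72.8 − 27.2 = 45.6 points wide, against 5 points for one regraded subject. PSSI and SSA, the other two primary measures, do not use this anchor.

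**The case for a change.** The strongest case for acting is that the label cannot be rescued by reading it as whole-body severity. No PGA or BSA minimum puts that reading into effect, so a subject with mild scalp disease and little body disease qualifies. The row is then wrong, or at best unsupported, on any scale. The anchor belongs to a primary measure that also decides entry. Appendix C allows some scaling at its almost-clear grade, so the two scales differ there as printed. The repair would be a few words.

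The factual core of this stands: the row describes a population that no criterion enforces, and the grade 1 text is faulty as printed. Its force is limited in four ways.

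- The row grades plaque psoriasis in general, while the criteria grade the scalp. It is a loose descriptor more than a competing rule. It is also wider than the criteria in one respect, because it omits scalp involvement and the 30% area.
- The harm from the label depends on a later report copying that row in preference to the criteria beside it.
- The missing word may be an effect of PDF reading. The synopsis text is visibly damaged, and the intended sense is clear either way.
- Appendix C is weak support. It is a separate whole-body scale whose grade 1 also allows possible plaque elevation, which Appendix A grade 1 does not. The two were not written to match sign by sign.

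**Conclusion.** No change to the plan follows. The population row is a clerical slip: one descriptive line against five consistent statements, with no effect on enrolment or analysis. A report that describes its subjects by the entry criteria and their baseline scalp IGA will be correct whatever the synopsis says. The grade 1 wording is a probable dropped connector that a trained rater would read as intended, and the averaging rule in Section 5.6.6 leads to the same grade. Tabulating IGA by baseline grade would correct no result.

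This rests on two assumptions: that sites enrol by the listed criteria, as Section 5.6.2 directs, and that raters apply the average-degree rule to mixed signs. Confidence is high for the label. It is moderate for the anchor, because the number of scalps that would fall in the literal gap cannot be derived from the documents, and whether the word is missing from the original page cannot be settled from this text. Each affected subject would move an IGA proportion by 5 points, small beside the sampling error at n = 20.

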2 ETHICS AND REGULATORY OBLIGATIONS

2.1 Institutional Review Board (IRB)

Written IRB approval of this protocol must be obtained before the study is initiated. Compliance with Title 21 of the US Code of Federal Regulations (CFR), Part 56, is required in order to protect the rights and welfare of human subjects involved in this study.

2.2 Ethical Conduct of the Study

The study will be conducted in accordance with the ethical principles that have their origins in the Declaration of Helsinki and its amendments. In addition, the study will be performed in compliance with Good Clinical Practices (GCP), including the archiving of essential documents.

2.3 Subject Information and Consent

The Informed Consent Form will be reviewed and approved by the IRB. The purpose, duration and possible risks and benefits will be explained to each potential subject. Consent in writing must be obtained from the subject before enrollment into the study. Consents will be signed and dated as required by Title 21 of CFR, Part 50. The consent will also comply with the requirements of the Health Insurance Portability and Accountability Act (HIPAA). The original, signed Informed Consent Form will be retained by the Investigator. A signed copy of the Informed Consent Form will be given to the subject. Each subject will be assigned a subject number that will be used in lieu of the subject's name on further research documentation.

3 INTRODUCTION

3.1 Overview of Psoriasis

Psoriasis is a chronic immunological disease characterized by infiltration of the skin with activated T cells and by abnormal keratinocyte proliferation and differentiation, resulting in marked inflammation and thickening of the epidermis. Psoriasis affects 1-3% of the world population, making it one of the most prevalent inflammatory immunological diseases.¹ There are several clinical subtypes of psoriasis: plaque, guttate, erythrodermic, inverse, and pustular. Plaque psoriasis is the most common type of psoriasis affecting 75-80% of psoriasis sufferers.² It presents as raised silvery scale, which can cover large areas, with underlying erythema, itching, and discomfort.

3.2 Rationale for Treating Scalp Psoriasis with Corticosteroid Topical Therapy

Scalp psoriasis can have a significant psychosocial impact on a patient's quality of life and the use of topical therapy has shown an increase in quality of life outcomes.³ Topical steroids play an important role in the long term management of psoriasis. Data from a study analyzing disease severity and patient treatment satisfaction revealed that patients with psoriasis are often dissatisfied with available treatments.⁴ Patient preferences of topical treatments can greatly impact compliance rates. Recent evidence shows that spray is a patient preferred vehicle more than 2 to 1 over creams, ointments, lotions, gel and foams.⁵ This study will analyze improvement in scalp psoriasis and patient outcomes.

4. STUDY OBJECTIVE

To explore the effectiveness and safety of Topicort® Topical Spray for patients with scalp plaque psoriasis.

5. INVESTIGATIONAL PLAN

5.1 Overall Study Design and Plan

20 subjects with at least mild scalp psoriasis and scalp surface area greater than or equal to 30%, will receive Topicort® twice daily for 4 weeks followed by twice daily two times a week for 12 weeks.

5.2 Study Population Criteria

Males and females ≥ 18 years of age with plaque type scalp psoriasis

5.2.1 Inclusion Criteria

Patients who meet all of the following criteria will be enrolled in the study:

1. Male or female adults ≥ 18 years of age.
2. Diagnosis of chronic plaque-type scalp psoriasis.
3. IGA of mild or greater (scalp only) determined at screening
4. Scalp surface area of 30% or greater determined at screening
5. Able to give written informed consent prior to performance of any study related procedures.
6. Females of childbearing potential (FCBP) must have a negative pregnancy test at Screening and Baseline. FCBP who engage in activity in which conception is possible must use one of the approved contraceptive options: hormonal contraception; intrauterine device (IUD); tubal ligation; or partner's vasectomy; Male or female condom, diaphragm with spermicide, cervical cap with spermicide, or contraceptive sponge with spermicide.
7. Subject must be in general good health (except for psoriasis) as judged by the Investigator, based on medical history, physical examination.

5.2.2 Exclusion Criteria

Patients will NOT be enrolled in this study if they meet any of the following criteria:

1. <30% scalp surface area
2. Scalp IGA clear or almost clear at time of screening
3. Any condition, which would place the subject at unacceptable risk if he/she were to participate in the study.
4. Pregnant or breast feeding, or considering becoming pregnant during the study.
5. Use of any investigational drug within 4 weeks prior to randomization, or within 5 pharmacokinetic/pharmacodynamic half lives, if known (whichever is longer).
6. Use of oral systemic medications for the treatment of psoriasis within 4 weeks (includes, but not limited to, oral corticosteroids, methotrexate, acitretin, apremilast and cyclosporine).
7. Use of ustekinumab and/or anti-IL-17 biologic therapy within 24 weeks or other experimental or commercially available biologic immune modulator(s) within 12 weeks prior to the first IP dose.
8. Patient used other topical therapies to treat within 2 weeks of the Baseline Visit (not including permitted topical therapy for face, groin and axilla).
9. Patient received UVB phototherapy within 2 weeks of Baseline.
10. Patient received PUVA phototherapy within 4 weeks of Baseline.
11. Patient has a known hypersensitivity to the excipients of Topicort Spray® as stated in the label.

5.3 Source of Subjects and Recruitment Methods

The Investigator will manage the recruitment of subjects upon approval of the study by the Institutional Review Board. Subjects may be recruited from internal patient lists and outside IRB approved advertisements.

5.4 Subject Enrollment and Treatment Assignment

20 subjects of either gender scalp plaque psoriasis will be enrolled to receive open-label Topicort® BID for 4 weeks followed by twice daily two days a week for 12 weeks.

5.5 STUDY TREATMENT

5.5.1 Topicort® Topical Spray 0.25% (desoximetasone)

5.5.1.1 Topicort® Description

Topicort® Topical Spray is a Class I, super-potent corticosteroid indicated for the treatment of plaque psoriasis in patients 18 years or older. Each gram of Topicort® Topical Spray 0.25% contains 2.5mg of desoximetasone in a clear, colorless liquid.

5.5.1.2 Topicort® Dosing Schedule

Topicort® will be supplied by Taro Pharmaceuticals U.S.A. Inc. and applied approximately 12 hours apart twice daily for 4 weeks followed by twice daily two times a week - on consecutive days - for 12 weeks (e.g. Saturday, Sunday). Patients will treat other body areas affected by plaque psoriasis with Topicort® during the study period (excludes face, groin, axilla).

5.5.1.3 Topicort® Dispensing and Dosing Record

Subjects will return all unused Topicort® to the study site. Site personnel will keep a record of Topicort® dispensed to and returned by each subject and note any missed doses.

5.5.1.4 Topicort Spray® Dosage Adjustments

If an SAE or an adverse event that is thought to be related to Topicort® and is not alleviated by symptomatic intervention, Topicort® will be discontinued. Subjects who permanently discontinue Topicort® therapy under this protocol should receive standard care of psoriasis treatment as prescribed by their physician.

5.5.2 Permitted Concomitant Therapy

Subjects may use non-steroidal topical medications to face, groin and axilla. Patients may apply Topicort Spray® on arms, legs and trunk to treat body psoriasis. Appropriate interventions (e.g., prescribed medications) may be performed as the investigator deems necessary to treat concomitant illnesses and/or safeguard the subjects' wellbeing. No investigational product or device may be used during the study.

5.6 Study Procedures

5.6.1 Informed Consent

This Study will be conducted in compliance with CFR Title 21, Part 50 (Informed Consent of Human Subjects). Informed consent will be obtained from each subject in writing before participation in the Study. A signed copy of the Informed Consent Form will be provided to each subject. A provision to obtain a signed authorization to provide protected health information to

the study sponsor, internal quality assurance agencies, health insurance agencies, and other parties as specified in the Federal Health Insurance Portability and Accountability Act (HIPAA) privacy regulation will be included in the Informed Consent Document. HIPAA authorization is voluntary. However, since the use and release of health information is critical to the conduct of the study, subjects who do not provide authorization to use and disclose their health information will not be enrolled into the study. Subjects who withdraw their authorization to use and release health information during study participation will be formally discontinued from the study. The investigator may use and release at any time all the information collected prior to a subject's withdrawal of the authorization to all authorized parties to satisfy scientific, regulatory, and financial concerns.

5.6.2 Inclusion and Exclusion Criteria

Subjects' eligibility to participate in the study will be determined according to the Inclusion and Exclusion Criteria during the screening period (0 – 30 days prior to the first dose of the study drug). Subjects who ultimately do not satisfy the eligibility criteria except changing treatments and undergoing a washout period, will not be enrolled into the study. Subjects who need to meet eligibility requirements will be asked to make the necessary changes. Subjects who agree and comply will be re-evaluated prior to Baseline. Subjects who meet the requirements at screening may be enrolled the same day.

5.6.3 Demographics and Medical History

The following information will be obtained for each subject during screening: date of birth, sex, race/ ethnic origin, relevant medical and surgical history, year of diagnosis of plaque psoriasis and scalp psoriasis, and current and previous anti-psoriasis treatments within the last 6 months. All current therapies for other medical conditions will be documented. Medical history will be reviewed and updated at the Baseline Visit to ensure that the patient remains eligible to participate in the study.

5.6.4 Urine Pregnancy Test

Pregnancy testing (urine β -human chorionic gonadotrophin [β -HCG]) will be conducted in all female subjects, except those without childbearing potential (e.g., one year post-menopause, post-hysterectomy, post-bilateral oophorectomy, etc) at Screening and Baseline Visit (Week 0) prior to the first dose of Topicort®. An interim urine pregnancy test may be performed if there is reason to believe the subject may have become pregnant during the study. Subjects with a positive pregnancy test will not be eligible to participate or to continue to receive study treatment.

